## Can the fluctuation observed in the endotracheal tube with compression applied to the epigastric region be used as a confirmation method for endotracheal intubation?

### STUDY PROTOCOL

This study was planned prospectively in the emergency department of a tertiary hospital. Ethics committee approval was obtained from the ethics committee of Düzce University (Date: 18/01/2021, Decision no: 2021/05). The relatives of the participants included in the study were informed about the procedure and written informed consent was obtained. The procedure does not pose any additional risk to the routine procedure and the question "Can the tube position be confirmed by epigastric manual compression method in addition to the currently used confirmation methods?" was sought.

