#### *Participants*

Patients admitted to the emergency department between 01/05/2021 and 30/05/2022, who were older than 18 years of age and who underwent ETE outside the hospital or within the first hour of arrival to the emergency department were included in the study. Patients in whom ETE was previously confirmed by USG or PETCO2, in whom elective intubation was decided, who were referred from another center, and who had known airway stenosis were excluded from the study. In the literature, it has been shown that >80% of ETE applications in the first attempt are successful [10,11]. This rate is 70% for out-of-hospital cardiac arrest cases [5]. In our clinic, an average of 300 ETE procedures are performed annually and the success rate is similar. Therefore, in order to include an equal number of successful and unsuccessful ETE procedures, the first 40 successful and the first 40 unsuccessful ETE procedures were included in the study. One participant from each group was excluded due to missing data.

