### ***Statistical analysis***

Descriptive statistics were presented as numbers and percentages. Demographic data were presented as mean±standard deviation (SD) for normally distributed variables and median, IQR (25-75%) for non-normally distributed variables. Pearson's chi-square test and Fisher's exact test (when the expected number of cells was less than five) were used for independent categorical variables. Bonferroni correction was used for subgroup analyses and  $p<0.016$  was considered significant. Sensitivity, specificity, positive likelihood ratio, negative likelihood ratio, positive predictive value and negative predictive value were calculated at 95% CI for the index tests of gastric compression fluctuation, epigastric sound and lung sounds based on the reference test of ultrasound confirmation. Statistical analyses were performed using IBM Corp. Released 2017. IBM SPSS Statistics for Windows, Version 25.0. Armonk, NY: IBM Corp. A P value less than 0.05 was considered statistically significant.

Confirmation was performed single-blind by emergency medicine specialists with at least 5 years of experience, without knowing who performed the procedure and where (in or out of the hospital). Confirmation was performed by auscultation of lung sounds (from the anterior and lateral sides of both lungs, upper and lower zones), evaluation of equal participation of both thoraxes in breathing by inspection, auscultation of the epigastric region, placement of capnography, monitoring of water vapor in the tube, manual compression of the epigastric region at least three times and evaluation of fluctuation in the tube, and pulse oximetry monitoring.

Epigastric compression was performed by applying pressure to the epigastric region at least three times with the volar side of the intubated patient while the patient was ventilated with a balloon-valved mask. During this procedure, the fluctuation of the air and fluid in the stomach inside the esophageal tube can be observed and its sound can be heard. It can be applied from the first inhalation.

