The USG procedure was evaluated by placing a linear ultrasound probe [SonoSite M-Turbo linear probe (13-6 MHz), Sonosite, Inc, Bothell, WA, USA] in the transverse position on the anterior side of the neck, just above the suprasternal notch, and observing the position of the tube (presence of a double path sign) and pleural sliding movement. While a single semicircular echogenic area is observed when the tube is in the trachea, a second semicircular echogenic area is observed when the tube is located in the esophagus.. USG was performed immediately after the ETE procedure. In patients in whom double pathway sign was observed and pleural sliding motion was not observed, the patient was re-intubated by the experienced specialist performing USG. It was confirmed by USG again. These procedures were categorized as "failed".

ETCO2 measurement by capnography was performed using a mainstream EMMA® Capnograph (PHASEIN AB Svärdevägen, Danderyd, Sweden) for intubated patients. It was assessed by the detection of PETCO2 greater than 5 mmHg after five breaths and the appearance of a typical square waveform.

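### Can the two-sign ultrasound rule for a failed intubation put the reference label at odds with tube position?

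*Combined protocol and SAP*

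**What the plan says.** The opening section (Study Protocol) puts the research question as "Can the tube position be confirmed by epigastric manual compression method", alongside the methods already in use.

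The ultrasound paragraph, which sits under the first Statistical analysis heading, says the examination consisted of "observing the position of the tube (presence of a double path sign) and pleural sliding movement". It says a single echogenic area is seen with a tracheal tube and that "a second semicircular echogenic area is observed when the tube is located in the esophagus". The one sentence that leads to a category starts "In patients in whom double pathway sign was observed and pleural sliding motion was not observed". Those patients were re-intubated, and the text continues "It was confirmed by USG again. These procedures were categorized as" *failed*. No sentence defines *successful*.

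The Participants section uses the same status to fill the two groups: "the first 40 successful and the first 40 unsuccessful ETE procedures were included in the study". One was then lost from each group for missing data, leaving 39 and 39. Both copies of the Statistical analysis section name ultrasound confirmation as the reference for sensitivity, specificity, likelihood ratios and predictive values of the three index tests. They do not say how the two ultrasound signs combine into that reference.

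**The concern.** The neck-view description attaches no condition about the pleura to an esophageal position, but the failed rule does. Read literally, with everything not failed taken as successful, a double-path tube with visible sliding joins the successful group although its neck view is the esophageal one.

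The compression paragraph explains the index sign by saying that "the fluctuation of the air and fluid in the stomach inside the esophageal tube can be observed". If such a tube fluctuated, the index test would agree with the neck view and still be scored as a false positive. Eligibility is broad ("who underwent ETE outside the hospital or within the first hour of arrival to the emergency department were included in the study"), and none of the exclusions removes the pattern.

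At stake is the 2x2 table behind all three index tests. With 39 in the successful group and few false positives expected, the positive likelihood ratio is the measure that would move most.

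**Working it through.** The plan states no figure to reproduce on this point. The check has two parts: the four sign patterns, then the size of the effect.

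**Patterns**

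| Double path | Sliding | Neck view | Meets failed rule | Conflict |
|---|---|---|---|---|
| yes | no | esophagus | yes | none |
| yes | yes | esophagus | no | yes, if counted as successful |
| no | yes | trachea | no | none |
| no | no | trachea | no | none (no category stated) |

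One pattern of the four is in question.

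**Inputs.** n = 40 − 1 = 39 per group (Participants), 78 in all. The number k of double-path tubes with sliding is not given and may be 0. Index sensitivity (Se) and specificity (Sp) are not given either, so values are assumed. Esophageal counts as positive. For the adverse case, the k tubes are assumed to be truly esophageal and counted as successful.

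**Perfect index test, k = 1, tube truly esophageal**
- Two-sign label: TP 39, FN 0, FP 1, TN 38. Specificity 38/39 = 97.4% (exact 95% CI 86.5 to 99.9%); LR+ = 1/(1/39) = 39.
- Neck-view label, same patients: TP 40, FN 0, FP 0, TN 38. Specificity 38/38 = 100% (90.7 to 100%); LR+ infinite.

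**Same tube, but the double-path reading is the false one and the tube is tracheal**
- Two-sign label: TP 39, FN 0, FP 0, TN 39, with no error.
- Neck-view label: TP 39, FN 1, FP 0, TN 38. Sensitivity 39/40 = 97.5%. The error has moved to the other label.

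**Imperfect index test, k tubes truly esophageal.** Apparent Sp = [(39 − k)·Sp + k·(1 − Se)]/39 and LR+ = Se/(1 − apparent Sp). For example, with Se 95%, Sp 98% and k = 1: (38 × 0.98 + 0.05)/39 = 95.6%, and LR+ = 0.95/0.0438 = 21.7.

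| Assumed Se / Sp | Measure | k = 0 | k = 1 | k = 2 | k = 3 |
|---|---|---|---|---|---|
| 95% / 98% | apparent Sp | 98.0% | 95.6% | 93.2% | 90.8% |
| 95% / 98% | LR+ | 47.5 | 21.7 | 14.0 | 10.4 |
| 80% / 90% | apparent Sp | 90.0% | 88.2% | 86.4% | 84.6% |
| 80% / 90% | LR+ | 8.0 | 6.8 | 5.9 | 5.2 |

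**Intervals for LR+.** Log method: SE = √(1/TP − 1/39 + 1/FP − 1/39), with expected counts TP = 39·Se and FP = (39 − k)(1 − Sp) + k·Se.
- Se 95%, Sp 98%, k = 0: TP 37.05, FP 0.78, SE 1.12; LR+ 47.5 (5.3 to 428).
- Se 95%, Sp 98%, k = 1: TP 37.05, FP 1.71, SE 0.75; LR+ 21.7 (5.0 to 94).
- Se 80%, Sp 90%, k = 0: TP 31.2, FP 3.9, SE 0.49; LR+ 8.0 (3.1 to 20.8).
- Se 80%, Sp 90%, k = 1: TP 31.2, FP 4.6, SE 0.45; LR+ 6.8 (2.8 to 16.2).

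In each pair, the estimate under one label lies well inside the interval under the other. For the perfect test, 97.4% lies inside the neck-view interval, while 100% lies just above the two-sign interval's upper limit of 99.9%.

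**The case for a change.** The strongest case for acting is that the text does contain the gap, the label feeds every accuracy measure, and a reader cannot tell from the documents how a discordant tube was handled. Defining *successful* and giving one count would settle it at almost no cost. If specificity is near 100%, a single such tube can more than halve the likelihood ratio.

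The gap stands, and so does the arithmetic. The inference to a wrong result does not.

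- The harm needs a default (not failed means successful) that no sentence states. A discordant tube could equally have been judged failed or left out.
- The rule may simply describe the usual picture of a failed tube, in which case the two sentences agree.
- The paragraph introduces ultrasound as two observations, and the analysis text names ultrasound confirmation as a whole as the reference. A two-sign label fits that. Preferring the neck view alone is a trade-off, since it carries the error itself whenever the double-path reading is false.
- The steep fall in LR+ reflects a cell with about one expected false positive. Any single misread for any reason would do the same. At 80% and 90%, one tube moves LR+ from 8.0 to 6.8, or 15%.

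**Conclusion.** No change to the plan follows. The documents leave one ultrasound pattern without an explicit category, but they do not show that following the plan gives a wrong answer. Three things would have to hold together: at least one such tube was enrolled, it was counted as successful, and it was in fact esophageal. The documents establish none of them.

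If all three held for one tube, a perfect index test would lose 2.6 points of specificity, and LR+ would fall from 47.5 to 21.7 or from 8.0 to 6.8 under the two assumed settings. Those shifts in LR+ are small beside the 95% intervals. If no such tube occurred, the effect is nil.

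The text is written in the past tense and already reports exclusions, so new wording would not alter the labels by which the two groups were filled. What remains is a missing detail that analysts can fill when they describe the reference standard and say how discordant signs were classified. This conclusion takes no side between the neck-view and two-sign labels and concerns only the analysis label, not the decision to re-intubate.

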### ***Statistical analysis***

Descriptive statistics were presented as numbers and percentages. Demographic data were presented as mean±standard deviation (SD) for normally distributed variables and median, IQR (25-75%) for non-normally distributed variables. Pearson's chi-square test and Fisher's exact test (when the expected number of cells was less than five) were used for independent

categorical variables. Bonferroni correction was used for subgroup analyses and  $p<0.016$  was considered significant. Sensitivity, specificity, positive likelihood ratio, negative likelihood ratio, positive predictive value and negative predictive value were calculated at 95% CI for the index tests of gastric compression fluctuation, epigastric sound and lung sounds based on the reference test of ultrasound confirmation. Statistical analyses were performed using IBM Corp. Released 2017. IBM SPSS Statistics for Windows, Version 25.0. Armonk, NY: IBM Corp. A P value less than 0.05 was considered statistically significant.
